3.2.2 Secondary Outcome Measures

Time-to-event outcomes (PFS at 2 and 3 years, TTNT, OS, TTLCB, duration of response, and time to response) will be analyzed according to the survival analysis methods. The quartiles with their 95% confidence interval (estimated using Kaplan-Meier methods and Greenwood's formula) will be presented. Kaplan-Meier plots with a 95% CI will be prepared. Estimates for the survivor functions for all time to event endpoints will be obtained by the Kaplan-Meier approach.

Cox regression analysis will be used to assess which variables are predictive of OS as well as to evaluate the association between early POD and OS from a risk-defining event, that is, survival from time of POD for early progressors or from 2 years after diagnosis.

Response rates (ORR, CR, CR30 and rate of patients with stable disease) will be presented with the number and proportions of responders and non-responders together with two-sided, 95% Clopper-Pearson CIs.

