6.2 POPULATION

The patient population taking part in the study will comprise patients aged ≥ 18 years with untreated advanced FL.

Patients must meet the following criteria for study entry:

1. Signed Informed consent according to local regulations, after performing at least 2 cycles of induction treatment with Obinutuzumab and chemotherapy, within 1 year from beginning of treatment;
2. Age ≥ 18 years;

Patients who meet any of the following criteria will be excluded from study entry:

1. Any contraindications to Obinutuzumab therapy according to local label for specific indication;
2. Concomitant participation in an interventional clinical study;
3. Patients not receiving treatment for untreated follicular lymphoma with Obinutuzumab according to standard of care and in line with the current summary of product characteristics (SmPC)/local labeling

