6.4.2 Data Collected during the Observation Period

During therapy with Obinutuzumab, laboratory assessments are routinely performed in accordance with current guidelines and local standard of care. When performed during the observational period, available results that represent an adverse event in accordance to CTCAE vs. 5, relevant symptom/signal of an event or abnormal laboratory finding that results in a change of the treatment in study will be documented in the eCRF. Most data will be documented during the treatment period when the respective assessments are usually performed according to standard of care. The proposed assessments and suggested timings for assessments in the protocol/observational plan are not mandatory. It is up to the treating physician to perform and document the assessments as performed in the real clinical setting.

In the routine care setting, patients are seen regularly by their treating physicians either for treatment or for regular assessment after treatment. Thus, no study-specific visits or evaluations are required by this protocol.

Tumor assessments collected in eCRF will comprise the following periods as available:

- Baseline tumor assessment
- During induction:
 - Mid induction: tumor assessment performed between cycle 2 and cycle 4 after the start of treatments
 - End induction: tumor assessment performed at the day of cycle 6 /8 (or when induction is early discontinued) until 2 month later
- After induction treatment:
 - 1 year after the start of treatment (from 10 to 14 months after the start of treatment)

- 2 years after the start of treatment (from 22 to 26 months after the start of treatment)
- 3 years after the start of treatment (from 34 to 40 months after the start of treatment)
- 1 year after end of maintenance as applicable
- Any tumor assessment, and the method used that shows disease progression, CR or CRu during induction or maintenance.

The lack of tumor assessments in those periods are not a protocol deviation as clinical practice should be followed.

Since the enrolment of patients into the study will occur after the treatment has already started (Patients included should have performed at least 2 cycles of induction treatment with Obinutuzumab but no later than the completion of 1 year of the treatment with Obinutuzumab), a retrospective data collection is expected.

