2. STUDY DESIGN

2.1 DESCRIPTION OF STUDY DESIGN

This is a retrospective and prospective primary data collection and secondary data use, non-interventional, multi-center, national (involving approximately 50 Italian centers) study.

Patients should be included after the start of treatment with Obinutuzumab and chemotherapy, including newly diagnosed FL patients. Patients included should have performed at least 2 cycles of induction treatment with Obinutuzumab and chemotherapy within 1 year from beginning of treatment and will be followed up 3.5 years from the start of treatment.

For each patient, the study will consist of a period of 42 months which can include:

- an induction treatment period (approximately 6 months) in which patients will receive Obinutuzumab and chemotherapy;
- a maintenance treatment period (approximately 24 months) in which patients will receive Obinutuzumab monotherapy;
- a follow-up period of one year, after the last Obinutuzumab administration, or up to 3.5 years after start of the treatment for early discontinued patients.

A schedule of activities is provided in Appendix 1.

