2.3 PRIMARY OUTCOME MEASURES

Progression of disease at 2 years (POD24), defined as the time from the date of treatment initiation with Obinutuzumab until the first documented progression of disease

or death due to disease progression, whichever occurs first, within 24 months from the start of treatment with Obinutuzumab. Patients who have no disease progression and have not died due to disease progression or who are lost to follow-up at the time of analysis will be censored at the date of last tumor assessment where no progression was documented or the last date of follow-up for disease, whichever is last. Patients without post-baseline tumor assessments will be censored at the time of their baseline visit unless death due to disease progression occurs prior to their first scheduled tumor assessment. Patients who die for reasons not related to the disease progression within 24 months from the treatment start with Obinutuzumab will be excluded from the statistical analysis of the endpoint.

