2.4 SECONDARY OUTCOME MEASURES

2.4.1 Secondary Effectiveness Outcome Measures

- Progression free survival (PFS) at 2 and 3 years, defined as the time from the date of treatment initiation until the first documented progression of disease measured by routine clinical care or death from any cause, whichever occurs first. Patients who have no disease progression and have not died or who are lost to follow-up at the time of analysis will be censored at the date of last tumor assessment where no progression was documented or the last date of follow-up for disease, whichever is last. Patients without post-baseline tumor assessments will be censored at the time of their baseline visit unless death occurs prior to their first scheduled tumor assessment;
- Time to next treatment (TTNT), defined as the Time to initiation of subsequent systemic anti-cancer therapy following initiation of Obinutuzumab containing therapy. Patients not starting a subsequent systemic anti-cancer therapy will be censored at the date of the last study visit;
- Overall survival (OS), defined as the time from initiation of study treatment to death from any cause. Patients who still alive at the time of analysis and patients who are lost to follow-up will be censored at their last time known to be alive;
- Correlation between POD24 and OS;
- TTLCB, defined as the time from first dose to loss of clinical benefit as assessed by the treating physician (single or multiple reasons possible: e.g. disease progression, deterioration in ECOG PS, death, other). Patients who do not loss clinical benefit will be censored at the date of the last study visit. Patients without post-baseline tumor assessments will be censored at the time of their baseline visit unless death occurs prior to their first scheduled tumor assessment;
- Overall response rate (ORR);
- Complete response (CR);
- Complete response at 30 months (CR30);

- Duration of response (DoR) measured per clinical practice, defined as the time from first documentation of CR or partial response (PR) (whichever occurs first) until disease progression, as evaluated by the physician according to routine clinical practice or death. Patients who have no disease progression and have not died or who are lost to follow-up at the time of analysis will be censored at the date of last tumor assessment where no progression was documented or the last date of follow-up for disease, whichever is last;

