3.2.1 Primary Outcome Measures

The primary endpoint is progression of disease at 2 years (POD24).

POD24 will be analyzed according to the survival analysis methods. The quartiles with their 95% confidence interval (estimated using Kaplan-Meier methods and Greenwood's formula) will be presented. Kaplan-Meier plots with a 95% CI will be prepared. Estimates for the survivor function will be obtained by the Kaplan-Meier approach.

Moreover, the POD24 will be analyzed as binary variable. Number and percentage of patients with its 95% CI for POD24 will be calculated.

Logistic regression analysis will be performed to assess which variables are predictive of POD24. To identify factors associated with POD24, logistic regression analysis will be performed with backwards selection (removing factors with $P > 0.05$). Univariable associations between factors and POD24 will be calculated by using the Chi-square test.

In the analysis of POD24 will be excluded patients who die within 24 months from the treatment start with Obinutuzumab for reasons not related to the disease progression.

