on treatment at the time of enrollment as part of their standard procedures for treatment. In case of patients enrolled after treatment completion, these data will be collected as indicated in the Retrospective column and the prospective information will be collected as described in the Follow-up period.

^b Approximately one-year follow-up after last dose of Obinutuzumab administration, as per clinical practice, or for patients that early discontinue the treatment up to 3.5 years after first treatment administration or until withdrawal of consent, study termination by the Sponsor, or death, whichever occurs first, regardless of whether patients start a new anti-cancer therapy. For patients that discontinue treatment before completing induction or maintenance, the follow up parameters can be collected in accordance with current patient's schedule visit and not every 2 months.

^c Patients included should have performed at least 2 cycles of induction treatment with Obinutuzumab and chemotherapy, within 1 year from beginning of treatment

^d Including any medication used by the patient from 7 days prior to starting treatment with obinutuzumab.

^e Laboratory tests will include: haematology (WBCs and differential count [at least neutrophils and monocyte %], RBCs, haemoglobin, haematocrit, platelet count) and blood chemistry (creatinine, beta-2 microglobulin, LDH, AST, ALT).

^f Data collected if performed per clinical practice as clinically indicated.

^g QoL will be completed prospectively period, every 2 cycles in induction treatment phase and every 2 months during maintenance treatment phase. For further instructions over QoL completion please refer to section 6.6.1. PRO questionnaires (FACT-Lym, EQ-5D) should be administered prior to any treatment assessments. PRO questionnaires should also be administered at first assessment after report of disease progression.

^h AEs/SAEs/IRR/ADR that occur prior ICF signature should be reported in eCRF as available; however only the event preferred term as per CTCAE vs 5.0 is required as Individual Case Safety Report are not applicable. Prospective safety that must be fully assessed and reported by study physician including assessment of seriousness (see Section 8.1.1.2), severity (see Appendix 3), and causality (see Appendix 3).

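### The POD24–OS Cox analysis times patients without early POD from 2 years after diagnosis, not from 24 months after first dose; with deferred treatment and the SAP 3.2.1 exclusion this pushes the hazard ratio upward, by an amount the documents cannot fix

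*SAP*

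**What the plan says.** SAP 3.2.2 and protocol 6.7.1 (secondary endpoints) plan, in identical words, a Cox analysis of early POD and OS that uses "survival from time of POD for early progressors or from 2 years after diagnosis". The second origin can only be meant for everyone who is not an early progressor. Early POD is not defined there; it is read here as POD24.

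Other places that bear on the point:

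- SAP 2.3 counts progression "or death due to disease progression, whichever occurs first, within 24 months from the start of treatment with Obinutuzumab".
- SAP 2.4.1 has "Overall survival (OS), defined as the time from initiation of study treatment to death from any cause". It lists the POD24–OS correlation as a secondary outcome, although no listed objective mentions it.
- SAP 3.2.1 has "excluded patients who die within 24 months from the treatment start with Obinutuzumab for reasons not related to the disease progression" for the POD24 analysis. SAP 3.2.2 does not say whether this carries over.
- SAP 3.2 and protocol 6.7.1 also give a general rule that event times run from enrolment, which is a third origin.
- Under SAP 2.1 patients "will be followed up 3.5 years from the start of treatment".
- Protocol 6.2 places consent "after performing at least 2 cycles of induction treatment with Obinutuzumab and chemotherapy, within 1 year from beginning of treatment"; protocol 6.4.2 has "no later than the completion of 1 year of the treatment with Obinutuzumab".
- SAP 1.1 and protocol 4 accept that patients without symptoms may stay untreated for years. SAP 2.5 collects the interval from diagnosis to treatment, but no expected value is given.
- SAP 3.4 plans no sensitivity analyses.

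**The concern.** Whether a patient is an early progressor is settled over the 24 months after first dose. The reference group's survival clock is tied to a different date. When treatment follows diagnosis by w months, the point 2 years after diagnosis falls w months before POD24 status is known; for w above 24 it falls before the first dose.

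A reference patient cannot die of progression in those w months, because that death would be a POD24 event. If the 3.2.1 exclusion applies, the patient cannot die of another cause either. The time is then event-free by construction (immortal time), and it is credited to the reference group alone.

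At stake is the hazard ratio for a listed secondary outcome. Part of it would reflect time before treatment rather than prognosis after progression.

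**Working it through.** **1. The plan's own figure.** The documents give no hazard ratio, death count or power for this analysis. The design figure reproduces: 13% of 300 is 39, the Clopper-Pearson limits are 9.41% and 17.34%, width 7.93% (stated 7.9%). That implies about 39 early progressors and 261 others.

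**2. Event-free time, from the documents.** Follow-up ends 42 months after first dose. On the treatment scale the reference clock starts at 24 − w and ends at 42, so it is 18 + w months long. Death is possible only in the last 18. The guaranteed share is w/(18 + w):

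- w = 12: 12/30 = 40%
- w = 24: 24/42 = 57%

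**3. Direction with the exclusion.** Take a common shift w. Reference deaths keep their number but move later. At each death of an early progressor, at least as many reference patients are at risk as before. At each reference death, no more early progressors are at risk than before. Every Cox score term rises or stays equal, so the hazard ratio rises.

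**4. Size under assumed fixed delays.** Simulation of 1,000,000 patients, 13% early POD, POD uniform over months 3–24, reference death rate 1–2% per year, true HR 1, 3 or 5, exclusion applied. Timing the reference from month 24 returns the true value. The current origin multiplies it by about:

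| Deferral | Multiplier |
|---|---|
| all, 1 month | 1.06 |
| all, 3 months | 1.17 |
| all, 6 months | 1.35 |
| all, 12 months | 1.8 |
| 20%, 12 months | 1.1 |
| 20%, 24 months | 1.3 |
| 20%, 36 months | 1.6–1.7 |

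**5. Size under assumed variable delays.** Exponential progression (13% at 24 months), exponential death (7% at 36 months), exponential waits in the stated share and 1.5 months in the rest, exclusion applied, no enrolment step. A true HR of 1 appears as:

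- all treated promptly: 1.08
- 20% wait a mean of 12 months: 1.20
- 20%, 24 months: 1.37
- 50%, 36 months (extreme): 1.95

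Repeat runs agree within about 0.04. Three-year mortality of 5% or 10% moves the values by at most about 0.03.

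**6. Without the exclusion.** True HR 5, setting of step 4, all reference patients deferred by 3 or 12 months. The multiplier depends on the rate of non-progression death in the window relative to the later reference rate:

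- half: 1.08 and 1.29
- equal: 1.00 and 1.01
- twice: 0.87 and 0.69

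The sign is therefore not fixed.

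**7. Enrolment.** If patients who progressed before consent are enrolled, they must have survived to consent, which biases the hazard ratio downward. True HR 1, setting of step 5, enrolment uniform over months 2–12 / all at month 12:

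| Analysis | Months 2–12 | Month 12 |
|---|---|---|
| Current text, prompt treatment | 1.00 | 0.91 |
| Current text, 20% wait 12 | 1.15 | 1.07 |
| Current text, 20% wait 24 | 1.31 | 1.21 |
| Origin corrected only | 0.91–0.95 | 0.80–0.85 |

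Origin correction plus delayed entry gives 0.97–1.03 in every scenario. If such patients are not enrolled, prompt treatment gives about 1.1 under the current text and delayed entry changes nothing.

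**8. Precision at 300 patients** (20% wait 24, with the enrolment step). Under the null there are about 11 deaths, 2 of them in early progressors, and the 95% limits lie a factor of 4.7–4.8 either side of the estimate. An estimate of 1.31 would run from 1.31/4.7 = 0.28 to 1.31 × 4.7 = 6.2. At a true HR of 5 there are 18–19 deaths and the factor is 2.7.

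**The case against.** The strongest reply is that the direction depends on two conditions: material deferral, and an exclusion that SAP 3.2.2 does not state. That is right. The exclusion is the natural reading, because those patients have no POD24 status, but it is not written down. A reader might infer that this study's hazard ratio will be inflated. The documents do not support that: with prompt treatment the shift is small, and if early other-cause deaths are kept the sign can reverse.

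A reader might also infer that, with prompt treatment, the origin and enrolment biases roughly cancel. That assumes that patients who progressed before consent are enrolled. Exclusion criterion 3 in protocol 6.2 bars patients not receiving obinutuzumab for untreated disease. SAP Appendix 1, footnote a ("In case of patients enrolled after treatment completion, these data will be collected as indicated in the Retrospective column") covers completion of treatment, not progression. The point is open.

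Nor should one infer that POD24 itself is safe in every respect. The origin error does not touch it. But if pre-consent progressors are left out, an assumed 13% would be observed as about 9% (enrolment over months 2–12) or 7% (month 12).

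Two further objections stand. Protocol 6.7 leaves detailed methods to the SAP, but protocol 6.7.1 itself contains the wording at issue, so a change in the SAP alone would contradict it. And the simulated repair contains no patients whose first POD24 event is death due to progression, so the size of that effect is not known.

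The low stakes are also fairly argued: the study is exploratory, with no formal hypothesis tests. That limits the priority; it does not make the origin right.

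**Conclusion.** The concern holds in conditional form. That the origin is inconsistent with the POD24 and OS definitions is clear from the text. That the hazard ratio is pushed upward follows if treatment was deferred and the 3.2.1 exclusion applies. Otherwise the direction is not determined. The size rests on assumed waiting times, mortality and enrolment timing, so steps 4 to 8 are illustrations and not estimates for this study. The bias is systematic, and nothing specified in the SAP would reveal it, but it is smaller than the random error of a single estimate. It should be fixed because the repair is cheap; it is not a major threat to the study. Confidence is high on the wrong origin, medium on direction and low on size.

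**What to change.** Change SAP 3.2.2 and protocol 6.7.1 together:

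- Replace the diagnosis-based origin with: *from 24 months after first obinutuzumab administration, in patients alive and progression-free at that date*. Keep the POD date as origin for early progressors.
- State that patients excluded under SAP 3.2.1, and patients censored progression-free before month 24, do not enter this comparison.
- State that this origin overrides the general enrolment origin in SAP 3.2 and protocol 6.7.1.
- Clarify whether patients who progressed before consent are eligible. If they are enrolled, let them enter the risk set at their enrolment date (delayed entry); correcting the origin alone would leave a null HR of about 0.8–0.95.
- Report patients whose first POD24 event is death due to progression as a separate count, and say that leaving them out lowers the hazard ratio.

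The cost is a few sentences and, if delayed entry is needed, a start-stop Cox model on dates the study already needs. The protocol wording needs the approval described in protocol 3. The intervals widen: with delayed entry, in the setting of step 8, the factor becomes 5.2–7.7 under the null and 2.9–3.1 at a true HR of 5. Under the null no hazard ratio was estimable in 27–31% of simulated studies, against 10–12% with the current text; at a true HR of 5 it was under 1% against 0%. At an assumed 5–15% censored before month 24, about 15–45 of 300 patients drop out of this comparison.

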For each patient, the study will consist of a period of 42 months which can include: an induction treatment period (approximately 6 months) in which patients will receive Obinutuzumab and chemotherapy followed by a maintenance treatment period (approximately 24 months) in which patients will receive Obinutuzumab monotherapy and a follow-up period of one year, after the last Obinutuzumab administration. Patients will be followed for 3.5 years after the first treatment administration regardless of early discontinuation of treatment for any reason in any timepoint. Patients who discontinue treatment for reasons other than disease progression (e.g., toxicity, AE) will continue to have their data collected for tumor assessments performed as per clinical practice, until disease progression, withdrawal of consent, study termination by the Sponsor, or death, whichever occurs first, regardless of whether patients start a new anti-cancer therapy.

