3.1 ANALYSIS POPULATIONS

The following populations will be considered for data analysis:

Effectiveness population

Effectiveness analysis population includes all patients who are enrolled and have received at least two cycles of Obinutuzumab.

Safety population

Safety analysis population includes all patients who are enrolled.

Screening failures are not considered for the analyses.

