3.4 SENSITIVITY ANALYSES

No sensitivity analyses are planned.

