3.6 HANDLING OF MISSING DATA

There will be no missing value handling mechanisms and missing data will not be imputed.

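### The SAP gives CR30 and the other time-specific response rates no denominator and no class for patients who progressed, died or were not assessed

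*SAP*

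**What the plan says.** The secondary objectives (SAP 1.2.1, item 3) ask for overall and complete response rates at mid and end of induction, during and after maintenance, and at 30 months (CR30). The analysis rule in SAP 3.2.2 is one sentence: "Response rates (ORR, CR, CR30 and rate of patients with stable disease) will be presented with the number and proportions of responders and non-responders", with exact 95% intervals.

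Other text that bears on the denominator:

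- SAP 3.1: "Effectiveness analysis population includes all patients who are enrolled and have received at least two cycles of Obinutuzumab".
- SAP 3.6: "There will be no missing value handling mechanisms and missing data will not be imputed".
- SAP 3.4: "No sensitivity analyses are planned".
- Protocol 6.4.2, on the assessment windows: "The lack of tumor assessments in those periods are not a protocol deviation as clinical practice should be followed".
- Protocol 6.1, on patients who stop treatment for reasons other than progression: they "will continue to have their data collected for tumor assessments performed as per clinical practice, until disease progression". The same section also states: "Patients will be followed for 3.5 years after the first treatment administration regardless of early discontinuation of treatment for any reason". The synopsis and Appendix 2 (note b) list tumor assessments among the minimum follow-up data, and note b continues follow-up whether or not new therapy is started.

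The time-to-event endpoints have censoring rules, and POD24 has an explicit exclusion for deaths unrelated to progression. The response rates have neither.

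**The concern.** A response rate at a late time point means little until one knows who is in the denominator. A patient who died at month 20 can have no record at month 30. A patient who progressed at month 15 will often have none, and if one exists it may reflect second-line therapy. A patient in remission may simply not have been scanned, which the protocol allows. The SAP leaves these cases open, and three readings are possible:

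1. **Available cases only.** This is the most literal reading of SAP 3.6. Failures without a record drop out, and the rate describes mainly patients who are still progression-free.
2. **All enrolled patients, with blanks as non-response.** This is itself a missing-data rule, and it turns unscanned remissions into failures.
3. **Any response on record.** Because follow-up continues after new therapy, a remission achieved with a later regimen could count as a CR30 responder.

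None of these reliably gives the proportion of the cohort in response after first-line treatment. CR30 and the post-maintenance rates are the ones at stake, because failures accumulate with time.

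**Working it through.** **The plan's own figures.** The plan states no precision for a response rate. Its Clopper-Pearson figures for N = 300 reproduce: POD24 of 13% (39/300) gives 9.4 to 17.3%, and 3-year PFS of 80% (240/300) gives 75.0 to 84.4%.

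**Inputs.** PFS is 90% at 2 years and 80% at 3 years (note to Protocol 6.7.5, Table 2), with N = 300. The complete response rate *c* among progression-free patients is not in the documents; I assume 70%, with a range of 50 to 90%.

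**Formulae.** Let S(t) be the share alive and progression-free at month t.

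- Rate if every failure is dropped: c
- Rate over the whole cohort with failures as non-responders: c × S(t)
- Overstatement: c × (1 − S(t)); as a ratio, 1/S(t)

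**Curves.** Curve A passes through both PFS figures with constant hazard between them, so S(30) = √(0.90 × 0.80) = 0.849, or 255 of 300. Curve B is a single exponential through 80% at month 36, so S(30) = 0.80^(30/36) = 0.830, or 249 of 300. Curve B gives 86.2% at month 24, not 90%, and serves only as a check on shape.

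**Upper bound by time, c = 70%, whole-patient counts, all failures dropped:**

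| Month | 1/S(t), A (B) | Overstatement in points, A (B) |
|---|---|---|
| 6 | 1.03 (1.04) | 1.9 (2.6) |
| 12 | 1.05 (1.08) | 3.5 (5.1) |
| 24 | 1.11 (1.16) | 7.0 (9.6) |
| 30 | 1.18 (1.20) | 10.5 (11.9) |
| 36 | 1.25 (1.25) | 14.0 (14.0) |

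**CR30, curve A, c = 70%.** There are 178 responders among the 255 progression-free patients.

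- All failures dropped: 178/255 = 69.8% (95% CI 63.8 to 75.4).
- All failures kept: 178/300 = 59.3% (53.5 to 64.9). This lies below the lower limit of the interval above.
- Half of the 45 failures kept: 178/277.5 = 64.1%, an overstatement of 64.1 − 59.3 = 4.8 points.

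Over c = 50 to 90%, the month-30 gap with all failures dropped is 7.5 to 13.5 points on curve A and 8.5 to 15.3 on curve B.

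**The opposite error.** Suppose 20% of the 255 progression-free patients have no scan, at random. The cohort rate is 0.70 × 255/300 = 59.5%. Counting blanks as non-response gives 0.70 × 0.80 × 255/300 = 47.6%, about 12 points too low.

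The effect of counting responses after second-line therapy cannot be sized from the documents.

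**The case against.** The strongest reply is that nothing in the plan removes anyone. The effectiveness population is all enrolled patients with at least two cycles, the result is a two-way split, and where the SAP wants patients excluded, as for POD24, it says so. The scan that shows progression during induction or maintenance is collected, as is survival status, and both are needed for PFS and OS. Known failures are therefore not missing data, and classing them as non-responders needs no imputation. The study is exploratory, and PFS, POD24, OS and duration of response are reported alongside.

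Much of this stands. A reader might infer that the plan drops progressed and dead patients, or that tumor assessments stop at progression for everyone. The documents do not support either. The until-progression sentence covers only patients who stop treatment for other reasons, and it sits beside text that follows all patients for 3.5 years. A reader might also take the 88.5% GALLIUM response rate from the protocol's background, apply it at year 3 and conclude that the rate will be 0.885 × (1 − 0.80) = 17.7 points too high. That is an upper bound: it assumes every failure is dropped, and it borrows a trial response rate as the rate among progression-free patients at year 3. Nor does the objective name years 1, 2 and 3; those windows come from the data-collection sections.

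What the reply does not supply is a rule. That failures can be classed does not mean they will be. The full-population reading still needs a decision on unscanned patients, which SAP 3.6 declines to make, and nothing bars a response to later therapy. Protocol 6.7.1 promises work on informative censoring and missing data; the SAP does not carry it through.

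**Conclusion.** The point holds as an undefined estimand, not as a demonstrated bias. The available-case reading would overstate CR30 by at most about 8 to 15 points, given the protocol's PFS, an assumed 50-90% complete response among progression-free patients, and no failure having a record in the window. At 70%, the overstatement is about 5 points if half the failures stay in and zero if all do. Through month 12 it is at most about 2 to 5 points at 70%, and a best-overall response would be little affected. The blanks-as-failures reading errs downward by an amount that depends on how often scans are missed. It would be wrong to say that the response rates in general will come out far too high. The choice matters for CR30 and the post-maintenance rates, and it should be made before the final analysis.

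**What to change.** In SAP 3.2.2 and 3.6, for CR30 and for ORR and CR at each time point after end of induction:

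1. Use the effectiveness population as the denominator.
2. Count progression, death or start of new anti-lymphoma therapy before the time point as non-response.
3. Show patients who are alive, progression-free and unscanned in the window as a separate 'not assessed' category.
4. Report beside this the rate among assessed patients plus failures.

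In the 20%-unscanned example, 51 patients would be shown as not assessed, and the rate in step 4 would be 0.70 × 204/(204 + 45) = 57.3%, close to the cohort value of 59.5%.

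The SAP should also say which assessment serves CR30. The yearly windows run from 22 to 26 months and then from 34 months, so none covers month 30 unless the end-of-maintenance assessment is meant.

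The cost is SAP wording and one derivation from progression, death and new-therapy dates already collected. The later response rates may look less favourable.
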